11. TREATMENT EVALUATION

11.1. Myelofibrosis

Table 15: Revised International Working Group for Myeloproliferative Neoplasms Research and Treatment (IWG-MRT) and European LeukemiaNet (ELN) response criteria for myelofibrosis.

Response categories	Required criteria (for all response categories, benefit must last for ≥ 12 weeks in order to qualify as a response)
Complete Remission (CR)	
Bone marrow: ¹ Age-adjusted normocellularity; <5% blasts; \leqGrade 1 myelofibrosis², AND
 
Peripheral blood: Hemoglobin ≥ 100 g/L and <UNL; Neutrophil count $\geq 1 \times 10^9$/L and <UNL; Platelet count $\geq 100 \times 10^9$/L and <UNL; <2% immature myeloid cells³, AND
 
Clinical: Resolution of disease symptoms; Spleen and liver not palpable; No evidence of EMH

Partial Remission (PR)	
Peripheral blood: Hemoglobin ≥ 100 g/L and <UNL; Neutrophil count $\geq 1 \times 10^9$/L and <UNL; Platelet count $\geq 100 \times 10^9$/L and <UNL; <2% immature myeloid cells³, AND
 
Clinical: Resolution of disease symptoms; Spleen and liver not palpable; No evidence of EMH, OR
 
Bone marrow: ¹ Age-adjusted normocellularity; <5% blasts; \leqGrade 1 myelofibrosis², AND
 
Peripheral blood: Hemoglobin ≥ 85 but <100 g/L and <UNL; Neutrophil count $\geq 1 \times 10^9$/L and <UNL; Platelet count ≥ 50 but <100 $\times 10^9$/L and <UNL; <2% immature myeloid cells³, AND
 
Clinical: Resolution of disease symptoms; Spleen and liver not palpable; No evidence of EMH

Clinical Improvement (CI)	The achievement of anemia, spleen or symptoms response without progressive disease or increase in severity of anemia, thrombocytopenia or neutropenia ⁴
Anemia response	
Transfusion-independent patients: a ≥ 20 g/L increase in hemoglobin level⁵
 
Transfusion-dependent patients: becoming transfusion-independent⁶

Spleen response ⁷	
A baseline splenomegaly that is palpable at 5-10 cm, below the LCM, becomes not palpable⁸, OR
 
A baseline splenomegaly that is palpable at >10 cm, below the LCM, decreases by $\geq 50\%$⁸
 
A baseline splenomegaly that is palpable at <5 cm, below the LCM, is not eligible for spleen response
 
Confirmation by MRI or CT showing $\geq 35\%$ spleen volume reduction is recommended (but not required)

Response categories	Required criteria (for all response categories, benefit must last for ≥ 12 weeks in order to qualify as a response)

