⁴ See table 15 for definitions of anemia response, spleen response and progressive disease. Increase in severity of anemia constitutes the occurrence of new transfusion dependency or a ≥ 20 g/L decrease in hemoglobin level from pre-treatment baseline that lasts for at least 12 weeks. Increase in severity of thrombocytopenia or neutropenia is defined as a 2-grade decline, from pre-treatment baseline, in platelet count or absolute neutrophil count, according to Common Terminology Criteria for Adverse Events (CTCAE) version 4.0. In addition, assignment to clinical improvement (CI) requires a minimum platelet count of $\geq 25,000 \times 10^9/L$ and absolute neutrophil count of $\geq 0.5 \times 10^9/L$.

⁵ Applicable only to patients with baseline hemoglobin of <100 g/L. In patients not meeting the strict criteria for transfusion-dependency at the time of study enrollment (see below), but have received transfusions within the previous month, the pre-transfusion hemoglobin level should be used as the baseline

⁶ Transfusion dependency before study enrollment is defined as transfusions of at least 6 units of packed red blood cells (PRBC), in the 12 weeks prior to study enrollment, for a hemoglobin level of <85 g/L, in the absence of bleeding or treatment-induced anemia. In addition, the most recent transfusion episode must have occurred in the 28 days prior to study enrollment. Response in transfusion dependent patients requires absence of any PRBC transfusions during any consecutive “rolling” 12-week interval during the treatment phase, capped by a hemoglobin level of ≥ 85 g/L.

⁷ In splenectomized patients, palpable hepatomegaly is substituted with the same measurement strategy

⁸ Confirmation of spleen or liver responses by imaging studies is recommended (but not required), where a $\geq 35\%$ reduction in spleen or liver volume, assessed by magnetic resonance imaging (MRI) or computed tomography (CT), is required for confirmation. Furthermore, a $\geq 35\%$ volume reduction in the spleen or liver, by MRI or CT, constitutes a response regardless of what is reported with physical examination.

Symptoms are evaluated by the Myeloproliferative Neoplasm Symptom Assessment Form total symptom score (MPN-SAF TSS). The MPN-SAF TSS is assessed by the patients themselves and includes fatigue, concentration,

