4.3. Major Secondary Endpoints

4.3.1. Definition

Spleen Response

Spleen response is defined as either a minimum 50% reduction in palpable splenomegaly of a spleen that is at least 10 cm at baseline or a spleen that is palpable at less than 10 cm but more than 5 cm at baseline becomes not palpable.

Transfusion Independence

Transfusion dependency is defined by a history of at least 2 units of red blood cell transfusions in the last month or a baseline hemoglobin level of less than 85 g/L that was not associated with clinically overt bleeding. For a transfusion dependent subject, transfusion independence is defined as he/she met either of the following conditions:

- Received no more than 1 unit of red blood cell transfusions in a rolling time interval of 30 days or more.
- Had a hemoglobin level increase over baseline more than 2g/dl if his/her baseline hemoglobin level was less than 85 g/L and received no transfusion.

Time to Response (TTR)

Time to response is defined as the duration from Study Day 1 to the earliest date that a response is first documented. For non-responders, it will be censored at the date of progressive disease/relapse or the date of the last adequate assessment, whichever comes first.

Duration of Response (DoR)

Duration of response is defined for responders as the interval from date of the initial documentation of a response to the date of first documented evidence of disease progression (or relapse for subjects who experience CR). For those subjects who are still without progression/relapse, DoR will be censored at the last adequate assessment.

Overall Survival (OS)

OS is defined as the interval from Study Day 1 to the date of death from any cause. Survival time of living subjects will be censored on the last date a subject is known to be alive or lost to follow-up.

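### SAP 4.3.1 lets low hemoglobin alone define transfusion dependence and accepts either of two independence conditions, so on its literal text an unchanged patient can be listed as having become transfusion-independent

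*SAP*

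**What the plan says.** **SAP 4.3.1.** Dependence is established by "at least 2 units of red blood cell transfusions in the last month or a baseline hemoglobin level of less than 85 g/L", with overt bleeding excluded. For a dependent patient, "transfusion independence is defined as he/she met either of the following conditions":

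- Condition 1: "Received no more than 1 unit of red blood cell transfusions in a rolling time interval of 30 days or more".
- Condition 2: "Had a hemoglobin level increase over baseline more than 2g/dl if his/her baseline hemoglobin level was less than 85 g/L and received no transfusion".

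**Protocol 16.4.3 and Appendix A.** Both use the same 2-unit, one-month criterion, but the units must have been given *for* a hemoglobin below 85 g/L. The two elements are required jointly.

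**Protocol Table 15 (IWG-MRT).** Footnote 6 is stricter. "Transfusion dependency before study enrollment is defined as transfusions of at least 6 units of packed red blood cells" within 12 weeks, for hemoglobin below 85 g/L. "Response in transfusion dependent patients requires absence of any PRBC transfusions during any consecutive" 12-week interval of the treatment phase, ending with hemoglobin of at least 85 g/L. Patients who are not transfusion-dependent are judged separately, by a rise of at least 20 "g/L increase in hemoglobin level". Footnote 5 limits that branch to baseline hemoglobin below 100 g/L and says which baseline to use "In patients not meeting the strict criteria for transfusion-dependency at the time of study enrollment" but recently transfused.

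**Status of the rule.** SAP 1.1 states the objective in terms of IWG-MRT criteria. The overview of protocol Section 16 says the SAP supersedes the protocol's analyses. SAP 4.3.2 plans a subject listing of transfusion-independence status. SAP 3.1 summarizes baseline transfusion dependence without a definition of its own.

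**The concern.** Replacing *for* with *or* turns one joint requirement into two alternatives. A patient who has never been transfused, or who receives a single unit a month, becomes transfusion-dependent through a low hemoglobin. Condition 1 then asks for no change from baseline and sets no hemoglobin floor, so that patient already satisfies it.

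Transfusion independence is one of the SAP's major secondary endpoints. A derived status that the patient can reach without any change does not separate benefit from no benefit. Because the SAP takes precedence, 16.4.3 does not correct the wording, and no other SAP section does.

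**Working it through.** The documents give no expected rate or sample size for this endpoint, so there is no figure to reproduce. The check applies each rule to patients whose condition does not change.

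**Rules.** U is units in the last month, Hb0 is baseline hemoglobin in g/L, and there is no overt bleeding.

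- Dependent, SAP: U ≥ 2 or Hb0 < 85.
- Dependent, 16.4.3: U ≥ 2, given for hemoglobin < 85.
- Dependent, footnote 6: at least 6 units in 84 days, for hemoglobin < 85.
- C1: at most 1 unit in some interval of 30 days or more.
- C2: Hb0 < 85, rise > 20 g/L, no transfusion.
- Independent, SAP literal: C1 or C2.
- Independent, SAP paired: C1 only for patients who qualified by units, C2 only for those who qualified by hemoglobin.
- Independent, footnote 6: 0 units in 84 days, ending at hemoglobin ≥ 85.

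**Results, hemoglobin constant at 80 g/L**

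| Transfusion pattern | Dependent: SAP / 16.4.3 / fn 6 | Independent: literal / paired / fn 6 |
|---|---|---|
| 0 units | yes / no / no | yes, day 30 / no / not applicable |
| 1 unit per 30 days | yes / no / no | yes, day 30 / no / not applicable |
| 2 units every 28 days, steady | yes / yes / yes | no / no / no |
| Same, with one 31-day gap | yes / yes / yes | yes / yes / no |

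The third pattern sits exactly at the footnote 6 threshold: 84/28 = 3 episodes, 3 × 2 = 6 units. A 31-day gap leaves 31 − 1 = 30 transfusion-free days and meets C1. A 30-day gap leaves 29 and does not.

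**Condition 2 on the literal reading.** No transfusion over 30 days or more means 0 ≤ 1 unit, so C1 is already met. Over any such period condition 2 adds no one, and the hemoglobin-rise requirement never operates.

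**The paired reading.** The first two rows no longer convert. But a never-transfused patient with hemoglobin below 85 g/L is still labelled transfusion-dependent, and a hemoglobin rise is labelled transfusion independence. Condition 2 is not the Table 15 anemia response either:

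| | SAP condition 2 | Table 15 |
|---|---|---|
| Baseline hemoglobin | < 85 g/L | < 100 g/L |
| Rise | > 20 g/L | ≥ 20 g/L |
| Duration | none stated | ≥ 12 weeks |

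**Illustration only.** Each hemoglobin-only patient would enter both numerator and denominator of any proportion. Assume 10 truly dependent patients, none of whom responds: 0/10 = 0% (exact 95% CI 0 to 30.8). Adding 3 unchanged hemoglobin-only patients gives 3/13 = 23.1% (5.0 to 53.8). Adding 1 gives 1/11 = 9.1% (0.2 to 41.3), and adding 5 gives 5/15 = 33.3% (11.8 to 61.6). The documents supply none of these counts.

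**The case against.** The best defence is that the paired reading is the natural one. At least 2 units a month mirrors at most 1 unit in 30 days, and low hemoglobin mirrors a hemoglobin rise. Condition 2 is expressly tied to baseline hemoglobin below 85 g/L, and the literal reading makes it redundant, which suggests that reading was not intended. This is a fair account of what the authors probably meant, but the text does not assign conditions to legs. The mislabelling of never-transfused patients and the mismatch with IWG-MRT remain on either reading.

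A second defence is that the SAP may supersede the protocol, and a 30-day rule fits a one-month dependence window. Departing from footnote 6 would indeed be permissible if declared. SAP 1.1, however, still promises IWG-MRT criteria. The irregular-gap example is constructed, and the documents do not show how often such gaps occur.

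Third, the practical weight is modest. This is a non-comparative study that the SAP calls a pilot, the status is only listed, and transfusion and laboratory data are listed too (SAP 4.3.3 and 5.3), so a reader could recheck it. All of this stands.

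Three stronger inferences are tempting but unsupported:

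- **A known inflation of the independence rate.** No count of hemoglobin-only patients is given, and the SAP plans no proportion.
- **Years of follow-up scanned for one favorable 30-day interval.** SAP 4.3.1 does not restate 16.4.3's limit to the first 9 cycles. But protocol Table 3 requires transfusion assessment only at screening and through Cycle 9, and a number of overlapping windows is not a misclassification rate.
- **A distorted primary endpoint.** SAP 4.2.1 uses the IWG-MRT and IWG criteria and, for Arm D, blast percentages. It does not use this rule.

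**Conclusion.** The definition is wrong as written and should be corrected. On the literal text, every non-bleeding patient with baseline hemoglobin below 85 g/L and 0 or 1 unit per 30 days, once observed for 30 days, is listed as moving from dependent to independent without any change. A patient steadily receiving at least 2 units in every 30-day window does not convert. On the paired reading the unchanged hemoglobin-only patient does not convert, but the dependence label and the independence standard are still not those the SAP says it uses.

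The consequence is limited to the listed status of one major secondary endpoint, any proportion later drawn from that listing, and possibly the baseline dependence summary in SAP 3.1. No eligibility criterion excludes the patients concerned, but their number is unknown, so the size of the effect cannot be stated. Confidence is high on the textual mismatch and does not extend to its numerical impact.

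**What to change.** Amend SAP 4.3.1 as follows.

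1. **Dependence.** Use one definition that requires transfusions: Table 15 footnote 6 if units over the 12 weeks before enrollment were captured. Otherwise use the 16.4.3 definition with *for*, labelled as not fully IWG-MRT.
2. **Independence.** Define it by Table 15 footnote 6 during the treatment phase. Report the Cycles 1–9 result from 16.4.3 as a stated time window, not as part of footnote 6.
3. **Hemoglobin response.** Delete condition 2 from transfusion independence. In Arms A, B, E and F, assess patients who are not transfusion-dependent by the Table 15 anemia response as written, including its baseline, rise and duration requirements. For Arm G use the Table 17 erythroid response, as 16.4.3 plans.

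**Cost.** SAP wording and reprogramming of one derived status. The transfusion assessments in Table 3 and the transfusion and laboratory listings in SAP 4.3.3 and 5.3 are the likely sources. Protocol Section 9 places blood products in the medical records, from the first treatment day. Table 3 states no look-back period for the screening assessment, hence the fallback in step 1.

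**Downsides.** Fewer patients will count as dependent, and rates will be lower. Nine uninterrupted 21-day cycles last 189 days and nine 28-day cycles 252 days. A 12-week interval must therefore begin by about day 189 − 84 = 105 or day 252 − 84 = 168, so later responses may not be confirmable within Cycles 1–9.

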Applicable Section(s)	Description of Change(s)
Rationale: To clarify and emphasize that additional hepatic laboratory surveillance is explicitly required for subjects in safety follow-up who had ongoing treatment-emergent abnormalities in LFTs or hepatic adverse events when imetelstat was discontinued,	
Figures 1-6	Revised “Event Monitoring” to “Event Monitoring/Hepatic Safety Monitoring” in the schematic diagrams for each treatment arm.
Rationale: To remove the limitation on duration of study treatment for patients who continue to derive clinical benefit beyond 3 years.	
Figures 1-6, footnotes 7.1.1.1 Arm A Treatment Schedule (footnote 1) 7.1.1.2 Arm B Treatment Schedule (footnote 1), 7.1.1.3 Arms C and D Treatment Schedule, (footnote 1) 7.1.1.4 Arms E and G Treatment Schedule, (footnote 1) 7.1.1.5 Arm F Treatment Schedule, (footnote 1) 8.1 Retreatment Criteria	Changed the possible duration of imetelstat study treatment beyond 3 years. Patients may continue to receive imetelstat study treatment for as long as they derive clinical benefit or until study end. The study will end when all subjects have discontinued study drug, the last patient enrolled has been treated for 5 years, or imetelstat is commercially available in the United States, whichever occurs first.
Rationale: The status of other imetelstat studies has changed.	
1.3.3 Clinical Experience with Imetelstat, Table 2	Database lock dates have been added for 4 Phase II imetelstat studies. The title of Study CP14B015 has been corrected to add “or Polycythemia Vera” and the study status has been changed from “Completed treatment (in safety follow up)” to “Completed”.

Rationale: To limit study procedures in the Extension Phase and at study completion to those needed for safety follow-up.

4 Test Schedule, Table 3	Physical examination for hepatomegaly and splenomegaly, and transfusion assessment removed as required assessments during the Extension Phase. Peripheral blood smear and IWG assessment of response removed as required assessments during the Extension Phase and at Study Completion/Early Termination. Urinalysis removed at Study Completion/Early termination.
4 Test Schedule, Table 3, footnote 9	Revised to delete chloride, bicarbonate, glucose, GGT, uric acid, amylase, and lipase from serum chemistry assessment.
4 Test Schedule, Table 3, footnote 10	Revised hematology assessment to replace differential count with absolute neutrophil count and to remove RBC count, MCV, MCH, MCHC, RDW, and MPV.

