4. TEST SCHEDULE

All routine assessments must be performed within \pm 3 days of the day indicated on the Visit Schedule (except for screening).

Table 3: Test Schedule: Core Phase = Cycle 1 – Cycle 9; Extension Phase = Cycle 10 and Beyond

Assessment	Screening (\leq 14 days Prior to registration)	\leq 24 hours before each imetelstat infusion Cycles 1-9 or end of cycle during interruption ¹	Weekly in first 2 cycles	End of Cycle 3	End of Cycle 9	Every Cycle in extension phase prior to infusion (Cycles 10 and beyond) ¹	At study completion or early termination (\pm 1 week) ²	Event Monitoring Every 3 mo until PD or subsequent treatment for MF Every 6mo after PD or subsequent treatment for MF ¹⁴
Physical examination including weight (height at screening) ^{3,4}	X			X	X		X	
Physical examination for hepatomegaly and splenomegaly ^{3,4}	X	X			X		X	
Transfusion Assessment	X	X						
Record adverse events ⁴	X	X			X	X	X	
Record concomitant medication		X				X	X	
ECOG performance status (Appendix D) ⁴	X	X			X		X	
12-lead ECG	X							
Chest x-ray	X							
Serum pregnancy test ^{4,5}	X	X				X		
Abdominal Ultrasound ⁶	X							
Urinalysis ⁷	X			X	X			

Assessment	Screening (≤14 days Prior to registration)	≤24 hours before each imtelstat infusion Cycles 1-9 or end of cycle during interruption ¹	Weekly in first 2 cycles	End of Cycle 3	End of Cycle 9	Every Cycle in extension phase prior to infusion (Cycles 10 and beyond) ¹	At study completion or early termination (± 1 week) ²	Event Monitoring Every 3 mo until PD or subsequent treatment for MF Every 6mo after PD or subsequent treatment for MF ¹⁴
Temperature and vital signs ⁸	X	X			X	X	X	
Serum chemistry ^{4,9}	X	X	X		X	X	X	
Serum calcium, phosphorus, magnesium, total protein	X			X	X		X	
CBC ^{4,10}	X	X	X		X	X	X	
Peripheral blood smear ⁴	X	X	X		X			
Serum Epo level	X			X	X			
International Working Group (IWG) Assessment of response ⁴		X			X			
INR (or PT) and aPTT ^{7,4}	X	X						
Bone marrow biopsy and aspirate with cytogenetic and JAK2 V617F studies ¹¹	X ¹²				X ^{12,13}			
Follow-up for survival and disease status and information of subsequent treatment for MF ¹⁴								X

R Samples may be used by Mayo Clinic or sponsor for research tests that include granulocyte JAK2V617F allele burden measurement, plasma cytokine analysis and other tests that are deemed insightful.

CBC = complete blood count

¹ In case of interruption, a cycle will be 3 months while treatment is held.

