- ⁹ Serum chemistries include sodium, potassium, BUN, creatinine, total and direct bilirubin, albumin, ALT, AST, alkaline phosphatase, LDH, and serum ferritin. In the event of new onset treatment emergent total bilirubin of Grade 2 or higher perform a reading of concurrent fasting bile acids and, to assess for hemolysis, a concurrent peripheral smear. Serum haptoglobin and reticulocyte count should also be performed if clinically indicated.
- ¹⁰ CBC must be repeated weekly in patients with treatment-emergent ANC $\leq 1.0 \times 10^9/L$ or platelet count $< 75 \times 10^9/L$. CBC includes hemoglobin, platelet count, WBC count, and absolute neutrophil count (ANC).
- ¹¹ If bone marrow biopsy and aspirate with cytogenetics and JAK2 V617F studies were performed as standard of care < 30 days prior to the patient signing consent procedure need not be repeated.
- ¹² Need to be submitted for central review. See Section 17 for details.
- ¹³ Only in patients achieving CI, PR or CR per IWG-MRT criteria (See Section 11) for Arms A, B,C, E, F and G, and for patients achieving $< 5\%$ peripheral blood blast percentage, for Arm D. The bone marrow examination can be performed earlier if patients were to achieve responses earlier or per investigator discretion. For the extension phase, only perform as clinically indicated.
- ¹⁴ Follow-up for survival status, disease follow-up status, notice of first relapse or progression in event monitoring phase, notice of first subsequent treatment and notice of new primary malignancy. Patients will be initially followed every 3 months (± 7 days) after study completion or early treatment termination until progressive disease or subsequent treatment for MF. Patients will then be followed every 6 months (± 7 days). Follow-up during the Event Monitoring Phase can be completed via telephone call. The Event Monitoring Phase of the study will be considered complete once the last patient has completed study treatment.

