9. ANCILLARY TREATMENT/SUPPORTIVE CARE

- Antiemetics may be used at the discretion of the attending physician.
- Patients should receive full supportive care while on this study. This includes blood product support, antibiotic treatment, and treatment of other newly diagnosed or concurrent medical conditions. All blood products and concomitant medications such as antidiarrheals, analgesics, and/or antiemetics received from the first day of study treatment administration until 30 days after the final dose will be recorded in the medical records.
- Diarrhea: This could be managed conservatively with loperamide. The recommended dose of loperamide is 4 mg at first onset, followed by 2 mg every 2-4 hours until diarrhea free (maximum 16 mg/day).
- In the event of Grade 3 or 4 diarrhea, the following supportive measures are allowed: hydration, octreotide, and antidiarrheals.
- If diarrhea is severe (requiring intravenous rehydration) and/or associated with fever or severe neutropenia (Grade 3 or 4), broad-spectrum antibiotics must be prescribed. Patients with severe diarrhea or any diarrhea associated with severe nausea or vomiting **should be hospitalized** for intravenous hydration and correction of electrolyte imbalances.

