16.4.3. Transfusion-Independence

Transfusion dependency is defined by a history of at least 2 units of red blood cell transfusions in the last month for a hemoglobin level of less than 85 g/L that was not associated with clinically overt bleeding (see IWG-MRT criteria; [Section 11](#)). The proportion of patients achieving transfusion independence during the first 9 cycles of treatment will be estimated by the number of patients who achieve transfusion independence divided by the total number of evaluable patients who were transfusion dependent at baseline. Ninety-five percent Clopper-Pearson exact

binomial confidence intervals for the true proportion of patients who become transfusion independent will be calculated. The same statistical method will be applied to anemia response for Arms A, B, E and F per IWG-MRT for myelofibrosis (Tefferi et al. 2013) and erythroid response for Arm G per IWG response criteria for MDS ([Cheson et al. 2006](#)).

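### SAP 4.3.1 drops the protocol's limits on the transfusion-independence interval, so it can fall where transfusions were not assessed

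*SAP*

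**What the plan says.** - **SAP 4.3.1 (Transfusion Independence).** The first of two alternative conditions is that the patient "Received no more than 1 unit of red blood cell transfusions in a rolling time interval of 30 days or more". No start, end, cycle limit or on-treatment restriction follows, and nothing requires the interval to be covered by assessments.
- **Protocol 16.4.3.** The endpoint is bounded: "The proportion of patients achieving transfusion independence during the first 9 cycles of treatment will be estimated", with an exact 95% confidence interval.
- **Protocol Table 15, footnote 6.** The IWG-MRT definition uses a rolling 12-week interval without red-cell transfusion and places it within the treatment phase.
- **Protocol Table 3.** The phases are "Core Phase = Cycle 1 – Cycle 9; Extension Phase = Cycle 10 and Beyond". The row "Transfusion Assessment" is marked at screening and in the Cycles 1–9 column (before each infusion, or at the end of a cycle during interruption). It has no mark for the extension phase, study completion or event monitoring.
- **Amendment 13 (5 October 2015).** Its change table agrees with current Table 3: "transfusion assessment removed as required assessments during the Extension Phase".
- **Table 3, footnote 14.** Event monitoring covers survival, disease status, first relapse or progression, first subsequent treatment and new malignancy. "Follow-up during the Event Monitoring Phase can be completed via telephone call".
- **Protocol section 9.** Blood products given from the first treatment day "until 30 days after the final dose will be recorded in the medical records".
- **SAP 4.1.2** says missing values are not imputed unless specified otherwise. **SAP 4.3.2** plans a listing of transfusion-independence status, and **SAP 4.3.3** a separate listing of transfusion data.
- **Protocol section 16** says the SAP supersedes the analyses in the protocol.

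**The concern.** In protocol 16.4.3 the period in which independence may be reached matches the period in which current Table 3 schedules the transfusion assessment. The SAP definition, which governs, loses that match. It counts units over any stretch of 30 days or more without asking whether anyone was recording units during that stretch.

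Improving anemia or inducing transfusion independence is a secondary objective in both documents, and the SAP places it under its major secondary endpoints. If unobserved time can pass as transfusion-free time, a patient can be listed as independent by staying under follow-up after assessment stops, with no change in transfusion need. Making the interval longer would not cure this: a 12-week interval searched over the same open-ended time has the same defect.

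**Working it through.** The plan gives no figure for this point, so the check compares texts and counts days.

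**1. Where may the interval lie?** Protocol 16.4.3: Cycles 1–9. Protocol Table 15 footnote 6: the treatment phase. SAP 4.3.1: no limit. The protocol's two limits differ from each other, but the SAP keeps neither.

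**2. Where are transfusions assessed on schedule?** Screening and Cycles 1–9. At scheduled cycle lengths that is 9 × 21 = 189 days (Arms A and B) or 9 × 28 = 252 days (28-day cycles). These are not upper limits, because a cycle lasts 3 months while treatment is held.

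**3. What does the rule return where nothing is collected?** The condition is units ≤ 1. With no recorded units the count is 0, and 0 ≤ 1 is true. The no-imputation rule does not clearly prevent this, because a transfusion that was never collected leaves no missing value, only the absence of a record.

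**4. Example.** A patient receives 3 units every 30 days, stops treatment in Cycle 3 and enters event monitoring. Contacts are every 3 months and do not ask about transfusions. Section 9 keeps blood products in the medical record until 30 days after the last dose. Beyond that, any 30-day stretch shows 0 units and meets the condition.

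**5. When does the gap exist on treatment?** Accrual closed on 22 January 2014, and Amendment 13 is dated 5 October 2015. The interval is 343 days to the end of 2014 plus 278 days in 2015, which is 621 days. Treatment had to begin within 7 days of registration, so even the last patient enrolled, if still treated, had at least 621 − 7 = 614 days before the change, more than 252. Patients on uninterrupted cycles had therefore passed Cycle 9 while the extension assessment was still required. The on-treatment gap arises mainly after October 2015. The event-monitoring gap does not depend on that date.

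**6. Comparison within SAP 4.3.1.** Time to response (for non-responders) and duration of response are both tied to the last adequate assessment. Transfusion independence has no such tie.

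**7. How much does the open end add?** This step rests on assumptions that are not in the documents: unchanged need, 2-unit episodes, gamma (shape 4) times between episodes, and 20,000 simulated patients per setting. With 2-unit episodes, having no more than 1 unit in 30 days means a gap of at least 30 days. The chance of such a gap inside the assessed core is:

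| Units per 30 days | 189 days | 252 days |
|---|---|---|
| 2 | about 0.99 | about 1.00 |
| 3 | about 0.8 | about 0.9 |
| 4 | about 0.4 | about 0.5 |

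If 30 unrecorded days are also searched, each figure becomes 1. The open end then adds about 0 to 0.01 at 2 units, 0.1 to 0.2 at 3 units, and 0.5 to 0.6 at 4 units. It matters most for the most heavily transfused patients. At 2 to 3 units the short interval already produces most of the false labels, which is a separate question.

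**The case against.** **The SAP never says that unrecorded time counts as transfusion-free.** This is correct; that step is an inference. A careful programmer could treat unassessed time as missing under the no-imputation rule. But the definition contains no coverage requirement, so the programmer would have to supply one.

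**No planned estimate is biased.** This stands. SAP 4.3.2 lists status only, without the protocol's proportion and confidence interval, and the transfusion listing lets a reader check each status.

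**The treatment-phase limit may still apply**, because SAP 1.1 states the objective per IWG-MRT criteria. This is possible. But SAP 4.3.1 writes its own definition, with a different interval length and unit allowance, and does not refer to Table 15, so the limit cannot be assumed to carry over.

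**Other sources remain on treatment.** Section 9 records may allow transfusions to be recovered until 30 days after the last dose, and concomitant medication is still recorded each extension cycle. This also stands in part. Neither document says these transfusions reach the eCRF in the extension, and no transfusion collection is specified for event monitoring after those 30 days.

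**A stronger reading to avoid.** A reader might set 189 to 252 days against a 5-year course and infer that nearly all the time searched is unassessed. The documents do not support that. The extension assessment was dropped only by Amendment 13, so the last patient enrolled, if still treated, had roughly 621 days under a required assessment, and patients enrolled earlier had more. A reader might also infer that almost no unchanged patient would qualify without the open end. Step 7 of the working shows otherwise for the SAP's 30-day interval.

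**Conclusion.** The point holds as a gap in the definition. The SAP removes both protocol limits and adds no requirement that the interval be assessed. Read literally, a 30-day stretch after the last assessment with no recorded units makes a still-dependent patient independent.

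The reach is event-monitoring time for any patient, and extension treatment mainly after 5 October 2015, where medical records may recover the data. The number of patients affected cannot be derived from the documents. It depends on how many dependent patients were followed past their last transfusion assessment and on how the count was programmed.

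The harm is to the listed status and to any rate derived from it, including the proportion that protocol 16.4.3 describes. It would be wrong to infer that a planned SAP proportion is biased, since the SAP plans none, or that every patient followed past Cycle 9 is misclassified. The change should be made, but the primary analysis is not affected.

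**What to change.** State in SAP 4.3.1 that:

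1. the whole rolling interval must lie between Study Day 1 and the last documented transfusion assessment on treatment;
2. time without transfusion assessment is not evaluable and does not count as transfusion-free;
3. the main definition uses the first 9 cycles, as in protocol 16.4.3;
4. independence first reached later, on documented extension data, is listed separately.

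Item 4 keeps the extension assessments made before Amendment 13 and respects the treatment-phase wording of Table 15, which a bare cut-off at Cycle 9 would not.

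The cost is a few sentences in the SAP and a coverage check in the derivation, with no new data collection. The downside is that independence first reached after Cycle 9 does not count in the main definition.
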